8.1.5 Statistical Analyses of Safety

Adverse events (AEs), laboratory data and vital signs are the primary safety parameters in this study. All safety comparisons will be performed within the safety analysis set.

Treatment-emergent AEs are defined as new events that begin either on or after the first dose of the study medication and within 70 days after the last dose of the study medication.

Treatment-emergent adverse events (AEs) will be summarized by treatment group using descriptive statistics. AEs, including serious AEs, AEs of special interest such as AEs leading to death and AEs leading to premature discontinuation (see details in the SAP), will be tabulated by system organ class and preferred term whereby the most current implemented MedDRA dictionary will be used. Also, summaries by severity and relationship to study drug will be done.

Other safety variables like laboratory data will be described by descriptive statistics as mentioned before. In addition, shift tables and listings will be provided for abnormal values, whereby the normal range of the analyzing laboratory will be used.

Details of this and all other analyses will be provided in the SAP.

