4.2 Design Diagram

Study M11-290 is a Phase 3, multicenter, randomized, double-blind study designed to evaluate the efficacy and safety of the human anti-TNF monoclonal antibody adalimumab in pediatric subjects with moderate-to-severe ulcerative colitis.

93 pediatric subjects with moderate-to-severe ulcerative colitis (Mayo score of 6 to 12 points with endoscopy subscore of 2 to 3) confirmed by colonoscopy with biopsy or flexible sigmoidoscopy with biopsy were to be enrolled at approximately 50 sites worldwide (Ex-Japan).

[figure not shown]
Prior to Amendment 4, subjects who met all of the inclusion criteria and none of the exclusion criteria were to be enrolled into the study and randomized 3:2 at Baseline to one of two double-blinded adalimumab induction doses (standard induction dose or high induction dose). The randomization was to be stratified by Baseline disease severity (Mayo score $[\le 9, > 9]$), prior exposure to anti-TNF and corticosteroid use at Baseline.

During the randomized double-blind induction period, subjects assigned to high dose (HD) group received adalimumab 2.4 mg/kg (maximum dose of 160 mg) at Baseline and at Week 1. At Week 2, subjects received adalimumab 1.2 mg/kg (maximum dose of 80 mg), followed by a dose of 0.6 mg/kg (maximum dose of 40 mg) at Weeks 4 and 6. Subjects randomized to standard dose (SD) group received adalimumab 2.4 mg/kg (maximum dose of 160 mg) at Baseline and matching placebo at Week 1, adalimumab 1.2 mg/kg (maximum dose of 80 mg) at Week 2, followed by a dose of 0.6 mg/kg (maximum dose of 40 mg) at Weeks 4 and 6.

After Amendment 4, subjects who met all of the inclusion criteria and none of the exclusion criteria were to be enrolled into the study and received open-label (OL) adalimumab high induction dose. During the open-label induction period, subjects received adalimumab 2.4 mg/kg (maximum dose of 160 mg) at Baseline and at Week 1. At Week 2, subjects received adalimumab 1.2 mg/kg (maximum dose of 80 mg), followed by a dose of 0.6 mg/kg (maximum dose of 40 mg) at Week 4 and Week 6.

Ongoing subjects randomized prior to Amendment 4 continued their blinded treatment during the induction period until Week 8.

Prior to Amendment 4, at Week 8, subjects demonstrating a clinical response per Partial Mayo Score (PMS) (defined as a decrease in PMS \geq 2 points and \geq 30% from Baseline)

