9.1 Study Drug Exposure

Induction study drug exposure will be summarized for ITT, ITT-E and safety population by treatment groups defined in Section 5.1. The study drug exposure during induction period does not include the dose received at Week 8. The duration of exposure during induction period will be calculated as follows:

Duration of induction-exposure = last induction dose date - first induction dose date + (max.*) 14 days

*cutting before first dose of study drug in the maintenance period.

Maintenance study drug exposure will be summarized for mITT, mITT-E, RR and safety population (restricted to subjects who received at least one dose of the study drug during maintenance phase). Of note, patients in this study don't receive study drug at Week 52, unless they roll over into Study M10-870, then this will be their first dose of study drug in Study M10-870 (and will be documented in Study M10-870, not Study M11-290). The duration of exposure during maintenance will be calculated as follows:

Duration of maintenance-exposure = last maintenance dose date (prior to potential re-randomization due to 1st disease flare) – first maintenance dose date + (max.*) 14 days

*cutting before first dose of study drug after re-randomization due to 1st disease flare, if applicable, or the first dose of study drug in Study M10-870, if applicable.

[figure not shown]
ADA exposure after re-randomization due to 1st disease flare for the RR population will be calculated as follows:

Duration of ADA exposure after 1st disease flare = last adalimumab dose date in the study after re-randomization due to 1st disease flare – first dose date of adalimumab after re-randomization due to 1st disease flare + (max.*) 14 days

*cutting before first dose of study drug in Study M10-870, if applicable

The overall adalimumab exposure (regardless of double-blind or open-label treatment or if it was rescue therapy after disease flare) will be summarized for the safety population. The duration of overall exposure will be calculated as follows:

- Subjects who are randomized to placebo at Week 8 and who have not been re-randomized due to a disease flare:
 - Overall ADA exposure = Duration of induction-exposure
- Subjects who are randomized to placebo at Week 8 and are re-randomized due to at least one disease flare during maintenance:

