11.2 Analysis of Adverse Events

Treatment-emergent AEs are defined as events with an onset date after the first dose of the study medication (i.e., on/after Rx Day 1) and with an onset date no more than 70 days after the last dose of the study medication. For subjects who roll over into the extension Study M10-870, the window ends prior to first dose date in Study M10-870 (but not more

than 70 days after the last non-missing injection date in Study M11-290). AEs with missing or unknown severity will be categorized as severe. AEs with missing or unknown relationship to study drug will be categorized as 'Reasonable Possibility' of being related to study drug. AEs that are reported more than 70 days after last dose of study drug will be excluded from the treatment-emergent AE summaries; however, they will be included in a separate AE data listing.

Separate Adverse Event Overview tables of number and percentage of subjects in the safety population with treatment-emergent AEs and events per 100 patient-years of induction-exposure and maintenance-exposure (as defined in Section 9.1) will be provided for events during induction period and events during maintenance period (prior to rerandomization due to disease flare if applicable), respectively. AEs that occur after the first dose of study drug in the maintenance period should not be considered treatment-emergent in the induction period, even if they occurred within 70 days of the last dose of study drug in the induction period.

The Adverse Event Overview tables for treatment-emergent AEs in maintenance period (prior to re-randomization due to disease flare if applicable) will also be provided for the RR population. Additionally, an Adverse Event Overview table of events after rerandomization due to first disease flare per 100 PYs of ADA exposure after first disease flare (as defined in Section 9.1) will be provided for the RR population by treatment groups with vs. without re-induction dose (as defined in Section 5.1).

Additionally, an Adverse Event Overview table of adalimumab-treatment-emergent events (i.e., during any ADA exposure throughout the study) per 100 patient-years of overall ADA exposure (as defined in Section 9.1) for patients in the safety population will be provided.

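### Adverse events in placebo-maintenance subjects from Week 8 to about Week 16 fall inside the SAP's own 70-day window after adalimumab, but the period tables show them only as placebo events, with no split

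*SAP*

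**What the plan says.** The protocol (8.1.5) counts new events as treatment-emergent if they begin on or after the first dose and "within 70 days after the last dose of the study medication". SAP 11.2 uses the same limit: "with an onset date no more than 70 days after the last dose of the study medication".

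SAP 11.2 then divides events by period. Its cut-off sentence reads "AEs that occur after the first dose of study drug in the maintenance period should not be considered treatment-emergent in the induction period", and continues "even if they occurred within 70 days of the last dose of study drug in the induction period". Maintenance events are tabulated up to any re-randomisation for flare. Under SAP 5.1 and 11.1, safety is analysed as treated, by treatment group, separately for induction and maintenance. A placebo-maintenance subject's events after the first placebo injection therefore go to the M-PL column.

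On dosing, both induction arms end with adalimumab: "followed by a dose of 0.6 mg/kg (maximum dose of 40 mg) at Weeks 4 and 6" (SAP 4.2). Maintenance starts with the next injection, since "The study drug exposure during induction period does not include the dose received at Week 8" (SAP 9.1).

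A separate table covers "adalimumab-treatment-emergent events (i.e., during any ADA exposure throughout the study", expressed per 100 patient-years of overall adalimumab exposure (SAP 11.2). For a placebo-maintenance subject who is never re-randomised, SAP 9.1 sets "Overall ADA exposure = Duration of induction-exposure". Induction exposure is the time from first to last induction dose plus at most 14 days, cut before the first maintenance dose.

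**The concern.** The period cut-off has no effect on drug attribution in the M-HD and M-SD arms, because those children stay on adalimumab. In M-PL alone it moves an event from a drug column to a placebo column while the plan's own window after adalimumab is still open. Two children with the same induction dosing and the same Week 9 infection are shown differently. A Week 8 non-responder's event stays in the induction table, because no maintenance dose closes the 70 days. An M-PL responder's event is shown as a placebo event.

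Safety is a stated objective, and M-PL is the only placebo group with safety data; the external placebo serves efficacy endpoints only (Protocol 5.6.2). With about 12 subjects, one subject with an event moves the M-PL percentage by 1/12, or about 8 points. If some early M-PL events are effects of the preceding adalimumab, the placebo rate is too high and the adalimumab arms look safer by comparison. No display or caveat in the SAP lets a reader see how many M-PL events arise in that interval.

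**Working it through.** **Size of the placebo arm.** SAP 4.3 presumes 12 internal placebo subjects and 57 adalimumab maintenance subjects out of 93, at a 75% Week 8 response. Check: (57 + 12) / 0.75 = 92, against the stated 93; conversely 93 × 0.75 − 12 = 57.75. The figures agree to within rounding, and the SAP Addendum also gives 12.

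**Length of the overlap.** Inputs: last adalimumab dose at Week 6 (day 42 from first dose; SAP 4.2), window of 70 days (SAP 11.2), first maintenance injection at Week 8 (day 56; SAP 4.2 and 9.1).

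- End of window: 42 + 70 = day 112, i.e. Week 16.
- Overlap with placebo: 112 − 56 = 56 days.
- With the ±3-day visit window applied to both dates: 50 to 62 days.

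**Share of one subject's placebo follow-up.** Share = min(56, follow-up) / follow-up, where nominal follow-up runs from Week 8 to re-randomisation or Week 52. Re-randomisation is possible from Week 12.

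| Placebo follow-up ends | Follow-up (days) | Share within 70 days of adalimumab |
|---|---|---|
| Week 12 | 28 | 28/28 = 100% |
| Week 16 | 56 | 56/56 = 100% |
| Week 18 | 70 | 56/70 = 80% |
| Week 26 | 126 | 56/126 = 44% |
| Week 52, no flare | 308 | 56/308 = 18% |

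**Share for the arm.** With 12 subjects and no flares: 12 × 56 / 365.25 = 1.84 of 12 × 308 / 365.25 = 10.1 patient-years, again 18%. The documents give no placebo flare rate, so anything else is assumed. Let a fraction f flare at Week t and the rest complete Week 52:

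share = [f × min(56, 7(t − 8)) + (1 − f) × 56] / [f × 7(t − 8) + (1 − f) × 308]

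For example, f = 0.5 and t = 18 gives 56 / (35 + 154) = 30%. With t at Week 12, 18 or 26:

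- f = 0.25: 21% to 23%
- f = 0.50: 25% to 30%
- f = 0.75: 33% to 43%

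Flares raise the share because they end placebo follow-up early. These are shares of patient-time. The documents do not allow a count of events.

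**The adalimumab-emergent table.** Take the Week 9 event, 21 days after the Week 6 dose, under each possible reading of the SAP.

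- *Literal reading, events during exposure as defined in SAP 9.1.* M-PL subject: exposure ends by Week 8, so the event is outside. Week 8 non-responder: exposure is last dose plus at most 14 days, also Week 8, so the event is also outside.
- *Reading with a 70-day tail.* Both events are inside. The cut-off sentence in SAP 11.2 governs only what is emergent in the induction period.

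Either way the two children are treated alike in this table. The asymmetry between them is confined to the period tables.

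**The case against.** The cut-off is deliberate and disclosed: the sentence itself acknowledges the 70-day overlap. It stops one event being counted in two period tables and applies equally to all three maintenance arms. Safety summaries are descriptive, and no confirmatory test depends on them. No event disappears, since each stays in the M-PL column and in the adverse event listings. All of this stands. It justifies keeping the as-treated column, but does not remove the need to show which M-PL events lie within 70 days of adalimumab.

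A reader might infer three stronger points, and the documents support none of them.

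- *That carry-over dominates the placebo column.* The overlap is 18% of follow-up without a flare. Higher figures for the arm depend on flare rates that the documents do not give.
- *That these events are drug effects credited to the wrong treatment.* Seventy days is the plan's collection and reporting window. Nothing in the documents shows that events within it are caused by adalimumab.
- *That M-PL children in particular drop out of the adalimumab total.* The SAP does not say whether that table carries the 70-day tail. On the literal reading, the loss affects anyone who stops adalimumab.

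It would also be wrong to mend the total by lengthening adalimumab patient-time for M-PL alone, because every other subject would keep a tail of at most 14 days.

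**Conclusion.** The point holds as a cheap and worthwhile improvement to the safety displays. Period tables built as SAP 11.2 describes will show M-PL events from Week 8 to about Week 16 only as placebo events, although they fall within the plan's own window after adalimumab. The share for an individual subject follows from the documents and nominal visit timing; the share for the arm rests on an assumed flare pattern. The effect on event rates cannot be sized from the documents. Its direction, a narrower adalimumab-versus-placebo contrast, applies only to the extent that events in the interval are carry-over. Separately, the numerator of the adalimumab-emergent table is ambiguous for every subject who stops adalimumab: two programmers could follow the SAP and reach different totals.

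**What to change.** In SAP 11.2, keep the as-treated M-PL maintenance column and add a display that splits its events and patient-time into two parts: up to 70 days after the last adalimumab dose, and later than that.

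In the same section, define adalimumab-emergent events as those with onset up to 70 days after the last adalimumab dose, for all subjects and whether or not placebo was given in between. In SAP 9.1, define the matching patient-time by one rule that applies to everyone.

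The cost is SAP wording and programming from dates already collected; no efficacy test changes. There are three downsides. The part of the M-PL column clear of the window becomes smaller. Some events appear in both an M-PL table and the adalimumab-emergent table, which needs a footnote. The adalimumab denominator grows: for 12 M-PL subjects who all reach Week 16 without a flare, from 12 × 56 / 365.25 = 1.84 to 12 × 112 / 365.25 = 3.68 patient-years, with further additions for other subjects who stop. That can lower the pooled rate per 100 patient-years and should be stated beside the table.

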11.3 Analysis of Laboratory Data

Hematology	Clinical Chemistry	Urinalysis ^a
Hematocrit Hemoglobin Red Blood Cell (RBC) count White Blood Cell (WBC) count Neutrophils Bands Lymphocytes Monocytes Basophils Eosinophils Platelet count (estimate not acceptable)	Blood Urea Nitrogen (BUN) Creatinine Total bilirubin Serum glutamic-pyruvic transaminase (SGPT/ALT) Serum glutamic-oxaloacetic transaminase (SGOT/AST) Alkaline phosphatase Sodium Potassium Calcium Inorganic phosphorus Uric acid Cholesterol Total protein Glucose Triglycerides Albumin	Specific gravity Ketones pH Protein Blood Glucose Others High-sensitivity C-reactive protein (hs-CRP) Antinuclear antibody (ANA) Anti-double-stranded DNA (anti-dsDNA) – if ANA positive β-HCG HBV C. difficile toxin

For selected continuous laboratory parameters, change from baseline to minimum (smallest) value, maximum (largest) value, and final value during induction, maintenance and overall ADA exposure, respectively, using safety population will be summarized by treatment group using descriptive statistics.

A listing of all subjects with any clinical laboratory determinations for selected laboratory parameters during each study period and during overall ADA exposure meeting criteria for potentially clinically importance (Common Toxicity Criteria [CTC] Grade \geq 3, based on the National Cancer Institute Common Toxicity Criteria for Adverse Event (NCI

[figure not shown]

CTCAE) scale, most recent version 5.0, see Table below) will be provided. For each of these subjects, the whole course of the parameter will be listed.

CTC Grading derived from NCI CTCAE v. 5.0

Test	Grade 1	Grade 2	Grade 3	Grade 4
Hemoglobin decreased	< LLN - 100 g/L	< 100 – 80 g/L	< 80 g/L	-
White blood cell decreased	$<$ LLN - 3.0 \times 10 9 /L	$< 3.0 - 2.0 \times 10^9 / L$	$< 2.0 - 1.0 \times 10^9 / L$	$< 1.0 \times 10^9/L$
Neutrophil count decreased	$<$ LLN - 1.5 \times 10 9 /L	$< 1.5 - 1.0 \times 10^9 / L$	$< 1.0 - 0.5 \times 10^9 / L$	$< 0.5 \times 10^9 / L$
Lymphocyte count decreased	$<$ LLN - 0.8 \times 10 9 /L	$< 0.8 - 0.5 \times 10^9 / L$	$< 0.5 - 0.2 \times 10^9 / L$	$< 0.2 \times 10^9/L$
Platelet count decreased	$<$ LLN - 75.0 \times 10 9 /L	$< 75.0 - 50.0 \times 10^9 / L$	$< 50.0 - 25.0 \times 10^9 / L$	$< 25.0 \times 10^9 / L$
Creatinine increased	> ULN - 1.5 × ULN	> 1.5 - 3.0 × baseline; > 1.5 - 3.0 × ULN	> 3.0 × baseline; > 3.0 - 6.0 × ULN	> 6.0 × ULN
Bilirubin increased	> ULN - 1.5 × ULN if baseline was normal; > 1.0 - 1.5 × baseline if baseline was abnormal	> 1.5 - 3.0 × ULN if baseline was normal; > 1.5 - 3.0 × baseline if baseline was abnormal	> 3.0 - 10.0 × ULN if baseline was normal; > 3.0 - 10.0 × baseline if baseline was abnormal	> 10.0 × ULN if baseline was normal; > 10.0 × baseline if baseline was abnormal
SGPT/ALT increased	> ULN - 3.0 × ULN if baseline was normal; 1.5 - 3.0 × baseline if baseline was abnormal	> 3.0 - 5.0 x ULN if baseline was normal; > 3.0 - 5.0 × baseline if baseline was abnormal	> 5.0 - 20.0 × ULN if baseline was normal; > 5.0 - 20.0 × baseline if baseline was abnormal	> 20.0 × ULN if baseline was normal; > 20.0 × baseline if baseline was abnormal
SGOT/AST increased	> ULN - 3.0 × ULN if baseline was normal; 1.5 - 3.0 × baseline if baseline was abnormal	> 3.0 - 5.0 x ULN if baseline was normal; > 3.0 - 5.0 × baseline if baseline was abnormal	> 5.0 - 20.0 × ULN if baseline was normal; > 5.0 - 20.0 × baseline if baseline was abnormal	> 20.0 × ULN if baseline was normal; > 20.0 × baseline if baseline was abnormal
Alkaline phosphatase increased	> ULN - 2.5 × ULN if baseline was normal; 2.0 - 2.5 × baseline if baseline was abnormal	> 2.5 - 5.0 × ULN if baseline was normal; > 2.5 - 5.0 × baseline if baseline was abnormal	> 5.0 - 20.0 × ULN if baseline was normal; > 5.0 - 20.0 × baseline if baseline was abnormal	> 20.0 × ULN if baseline was normal; > 20.0 × baseline if baseline was abnormal

Shift tables from baseline to worst CTC grade during induction, maintenance and overall ADA exposure will be provided for selected laboratory parameters.

Additionally, for selected laboratory parameters, shift tables from baseline to each period will be provided to cross classify subjects from baseline to induction, maintenance, and during the overall ADA exposure by the presence of clinically significant laboratory. Each subject's baseline value will be categorized as clinically non-significant (CTC Grade \leq 3) or clinically significant (CTC Grade \geq 3). During induction, maintenance, or during the overall ADA exposure, the subject's value will be classified as all values non-significant or at least one value clinically significant. Rows of the shift table will categorize baseline (non-significant, significant), and columns will categorize induction, maintenance, or during the administration of adalimumab status (all non-significant, at least one significant).

[figure not shown]
The liver-specific laboratory tests include the serum glutamic pyruvic transaminase (SGPT/ALT), serum glutamic-oxaloacetic transaminase (SGOT/AST), alkaline phosphatase, and total bilirubin. A listing of potentially clinically significant liver function laboratory values will be provided. The listing will include all subjects who met any of the following 4 criteria:

- ALT \geq 3.0 × ULN, or
- AST \geq 3.0 × ULN, or
- Alkaline phosphatase $\geq 1.5 \times ULN$, or
- Total bilirubin $\geq 2.0 \times ULN$.

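### The protocol promises shift tables and abnormal-value listings on the laboratory normal range, but SAP 11.3 grades only 10 of 27 hematology and chemistry tests, each in one direction, so 17 tests have neither

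*SAP*

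**What the plan says.** Protocol 8.1.5 counts laboratory data among the primary safety parameters and commits to a range-based display: "In addition, shift tables and listings will be provided for abnormal values, whereby the normal range of the analyzing laboratory will be used". It then leaves the particulars to the analysis plan: "Details of this and all other analyses will be provided in the SAP". The protocol synopsis also promises shift tables, without saying on what scale.

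SAP 11.3 repeats the laboratory panel and specifies these outputs:

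- A shift table on the worst grade reached: "Shift tables from baseline to worst CTC grade during induction, maintenance and overall ADA exposure will be provided for selected laboratory parameters".
- A second shift table for selected parameters, dividing subjects at CTC Grade 3.
- A listing of subjects who reach Grade 3 or higher on selected parameters.
- A listing of liver results at or above stated multiples of the upper limit of normal (ALT, AST, alkaline phosphatase, total bilirubin).
- Descriptive change from baseline to each subject's lowest, highest and final value, again for selected parameters.

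The grades come from one table, headed "CTC Grading derived from NCI CTCAE v. 5.0". The selected parameters are not named anywhere in the section.

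**The concern.** A shift table or threshold listing needs a rule that puts each result in a category. The protocol names a rule that exists for every quantitative test, the laboratory's own normal range. The SAP uses a rule that exists only for tests with a row in its grading table. If that table is much shorter than the panel, the SAP cannot produce what the protocol describes for the remaining tests, whatever a programmer later decides to select.

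At stake is the visibility of individual abnormal values in a pediatric trial of 93 subjects treated for up to 52 weeks. Range-based shift tables show how many children moved outside the normal range, and in which direction. A summary of changes does not give that count. No efficacy conclusion depends on the point.

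**Working it through.** The plan states no figure to reproduce. The check is a count, followed by a comparison of outputs.

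**Panel (SAP 11.3; same tests as Protocol Table 2).**
- Hematology: "Hematocrit Hemoglobin Red Blood Cell (RBC) count White Blood Cell (WBC) count Neutrophils Bands Lymphocytes Monocytes Basophils Eosinophils Platelet count (estimate not acceptable", which is 11 tests.
- Chemistry: BUN, creatinine, total bilirubin, ALT, AST and alkaline phosphatase (6), then "Sodium Potassium Calcium Inorganic phosphorus Uric acid Cholesterol Total protein Glucose Triglycerides Albumin" (10), so 6 + 10 = 16.
- Total: 11 + 16 = 27.

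**Grading table (SAP 11.3).**
- Decrease only: hemoglobin, white cells, neutrophils, lymphocytes, platelets (5).
- Increase only: creatinine, bilirubin, ALT, AST, alkaline phosphatase (5).
- Total: 5 + 5 = 10, none graded in both directions.

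**Tests without a grade.**
- Hematology, 11 − 5 = 6: hematocrit, RBC, bands, monocytes, basophils, eosinophils.
- Chemistry, 16 − 5 = 11: BUN, sodium, potassium, calcium, inorganic phosphorus, uric acid, cholesterol, total protein, glucose, triglycerides, albumin.
- Total: 27 − 10 = 17, and 17/27 = 63%.

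The six urinalysis items also have no grading row. Including them gives 17 + 6 = 23 of 27 + 6 = 33.

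**Does another laboratory output cover the 17?**

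| SAP 11.3 output | Rule | Can it classify the 17? |
|---|---|---|
| Worst-grade shift table | CTC grade | No, there is no grading row |
| Shift table split at Grade 3 | CTC grade | No |
| General listing | CTC Grade 3 or higher | No |
| Liver listing | Multiples of ULN | No, all four tests are among the 10 |
| Change to minimum, maximum, final | None (continuous) | Summarized if selected, not classified |

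**How far are the graded 10 covered?** For the five hematology tests and creatinine, Grade 1 begins at the lower or upper limit of normal. The same holds for the four liver tests when baseline is normal. In the graded direction the worst-grade table therefore keeps a normal-range boundary. Three gaps remain:

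- The opposite direction has no grade, so a raised white cell or platelet count is never classified.
- For the four liver tests with an abnormal baseline, grades are multiples of the subject's own baseline. The baseline value itself falls in no grade.
- The general listing starts at Grade 3. For the five hematology tests and creatinine, a subject who reaches only Grade 1 or 2 is not listed.

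As printed, the two categories of the second shift table both include Grade 3. That may come from text extraction, and nothing here rests on it.

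**The case against.** The strongest case against is that the protocol delegates detail to the SAP, and that concentrating categorical output on graded hematologic and hepatic thresholds is a defensible choice. Some ungraded tests overlap graded ones (hematocrit and RBC with hemoglobin, bands with neutrophils), so 63% gives equal weight to tests of unequal interest. Listing every out-of-range value over 11 scheduled laboratory time points would be long. Much of this stands as a reason to keep the CTC outputs and to treat the matter as moderate. It does not answer the mismatch: delegating detail lets the SAP say how the normal range will be used, but SAP 11.3 leaves most of the panel with no category boundary at all.

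A reader might also infer more than the documents support:

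- **That an out-of-range value in one of the 17 tests is counted and listed nowhere, or at most shifts a mean.** Under Protocol 6.1.1.1 a laboratory abnormality is an adverse event if it leads to discontinuation, needs medical intervention, or is judged one by the investigator. SAP 11.2 counts and lists adverse events. SAP 6.0 includes the minimum and maximum in continuous summaries, so an extreme change in a selected test would show. SAP 10.4 analyzes change in albumin, total protein, hematocrit and RBC, four of the 17.
- **That the SAP concealed a change.** SAP Section 12 is a high-level account of revisions to the SAP after protocol amendments. It is not a register of departures from the protocol, and its silence proves nothing.
- **That Protocol 8.1.5 itself demands low/normal/high tables for all 27 tests.** It refers to abnormal values and the laboratory range, with no list of tests and no table layout.
- **That heavy corticosteroid use makes the gap worse.** Baseline use is permitted and was a stratification factor, but no proportion is given.

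**Conclusion.** The mismatch is real. As written, SAP 11.3 cannot deliver the range-based shift tables and abnormal-value listings of Protocol 8.1.5 for 17 of 27 hematology and chemistry tests, or for the ungraded direction of the other 10. For those 10 it meets the commitment in part.

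What is lost is the tabulation and listing of out-of-range results that did not become adverse events. That deserves correction because laboratory data are a named primary safety parameter.

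The conclusion rests on two readings. First, 27 means hematology plus chemistry, leaving out urinalysis and the miscellaneous tests. Second, selecting a test for a CTC-based display cannot classify it when the SAP gives it no grades.

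**What to change.** Add to SAP 11.3:

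1. Low/normal/high shift tables on the central laboratory's range, from baseline to the lowest and to the highest value in each period (induction, maintenance, overall adalimumab exposure).
2. A listing of values outside that range.
3. Scope for both: at least the 17 ungraded tests and the ungraded direction of the 10 graded tests.
4. The names of the parameters meant by selected in each existing output.

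Keep the CTC shift tables, the Grade 3 listing and the liver listing. The cost is SAP wording plus additional standard tables and listings from central-laboratory results already collected under the protocol. No new data, visits or samples are needed, and no confirmatory analysis changes.
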